### **Pilot study to investigate hypoglycemia-induced thrombotic potential**

Funding for this part is not sought and therefore no details are given (can be provided if requested).

### **Statistical analysis**

The observational part of the study will collect various data and will be the basis for future studies. Power calculations were based on the interventional study. Given our current data showing a death rate in excess of 17% within one year of hypoglycemia, we calculated that 200 individuals are needed in each of the study arms to detect a drop in mortality to 10% in intensively monitored patients (at  $p=0.05$ ). Between group analysis will be done using unpaired  $t$ -test for normally distributed data and the non-parametric Mann-Whitney test will be used for data that are not normally distributed. For categorical data, 2X2 contingency tables will be used and multiple regression analysis will be performed to determine potential causes of hypoglycemia.

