**PI: [name]**

**Co-Investigators: [name], [name]**

**Statistical analysis: [name]**

## **Background**

Hypoglycemia is a common complication of diabetes treatment, particularly when glucose control is intensified (1-3). Until recently, hypoglycemia was regarded as an acceptable "side effect" of glucose lowering therapy, given the benefits of tight glycemic control at reducing microvascular, and to some extent macrovascular, complications of diabetes (2-7). However, studies in the past few years have demonstrated that hypoglycemia is probably a more serious side effect than initially thought (8-11). A major warning as to the potential dangers of hypoglycemia was delivered in the ACCORD study (12), when excess mortality was demonstrated in the intensive glucose arm of the trial, necessitating study termination and fuelling speculation about the role of intensive glucose control in the management of diabetes. The fear of hypoglycemia-induced death in diabetes is not unfounded as there are clear mechanistic pathways to explain this link. Hypoglycemia is associated with repolarisation abnormalities in the heart and increased thrombosis potential as we and others have shown (13-15). Indeed, large scale studies and anecdotal reports have shown associations between acute cardiac events/mortality and hypoglycemic events (11,16-18). Moreover, our preliminary data in Leeds have revealed that severe hypoglycemia, requiring emergency services intervention in 856 patients, is associated with 17.1% mortality within 12 months of the event (unpublished data). This death rate is comparable to diabetes patients sustaining acute cardiac ischemic event in Leeds, which currently stands at 15.8% (19). Also, the mean age of the diabetes cohort was only 61 years, and therefore the high death rate following hypoglycemia is certainly a major cause for concern (for gender and diabetes type distribution, see Figure 1). Moreover, our data showed that in excess of 200 individuals had recurrent severe hypoglycemic events, despite local pathways designed to ensure higher levels of clinical support. Interestingly, of the type 2 diabetes subjects, 28% were not on insulin, being managed with oral hypoglycemic agents (95% treated with sulphonylureas). The degree of documented hypoglycemia in this group was comparable to individuals on insulin therapy with glucose levels at the arrival of ambulance crew of  $1.8 \pm 1.1$  and  $1.9 \pm 0.7$  mmol/l, respectively ( $p > 0.1$ , unpublished data).

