
**Figure 1.** Type of diabetes and gender distribution of individuals with severe hypoglycemia requiring emergency services intervention in Leeds (1307 events).

It is unclear at this stage whether the observed increased mortality following severe hypoglycemia is directly related to low plasma glucose or whether severe hypoglycemia is more likely to occur in individuals with terminal clinical conditions (20), which may be due, for example, to weight loss and/or decreased appetite. Naturally, this needs to be clarified as it has important clinical implications for the treatment of these individuals.

Studies on the occurrence of severe hypoglycemia in the community have been both limited and incomplete. In particular, the predictors of severe hypoglycemia

in the community have not been fully evaluated, which is partly due to the inadequate methodologies used or the inappropriate statistical methods employed (21-23). A recent retrospective observational study, conducted in Australia, has shown that duration of insulin treatment, renal factors and diabetic neuropathy are some of the predictors of severe hypoglycemia (24). Furthermore, this study has demonstrated that high HbA1c levels are not necessarily associated with lower risk of severe hypoglycaemia. It remains unclear, however, whether infrequent blood glucose testing and inadequate clinical support has a role in increasing the risk of severe hypoglycemia, whereas the effect of co-morbidities requires further clarification. For example, any clinical condition that is associated with weight loss or reduced appetite may be contributing to hypoglycemia. Another example is excess alcohol intake, which may also result in frequent and severe hypoglycemia (more details are provided below).

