as dietitian support may be sought if the research nurse and/or PI find this to be necessary. In cases of newly diagnosed (or suspected) clinical conditions, referrals to an appropriate specialty will be made after review by the PI. If social circumstances are found to be inappropriate, for example in the case of older individuals not managing on their own, the physician in charge of the patient will be informed and steps will be taken to provide support according to the need of each individual.

In summary, the research nurse will concentrate on establishing the cause of the severe hypoglycemic episode and together with the PI will alter treatment, involve other diabetes/non-diabetes disciplines as appropriate and introduce changes to social support as required.

The research nurse will contact the patient weekly for the first month, every two weeks for the following month followed by contact at months 3, 6 and 12. Face to face contact with the patient will be arranged at enrolment, 1, 3 and 12 months. Patient will be asked to fill in the questionnaire at enrolment and end of 3rd month, with selected patients asked to complete the form again at 12 months (explained in Figure 4). Blood tests will be arranged as detailed above. In the standard arm, patient will be contacted only once as per current arrangement and subsequent treatment left to the discretion of the attending physician (summarised in Figure 4).

**Figure 4.** Summary of the preliminary interventional part of the study. U&Es: urea and electrolytes, LFTs: liver function tests, UACR: urinary albumin/creatinine ratio, MACE: major adverse cardiovascular events, m:

month, d: day. Questionnaire will be done at enrolment and 3 months in both groups. If a significant difference exists between the two time points in the same patient, the questionnaire will be repeated at 12 months. Clinical outcome at 12 months will also include frequency of hypoglycemia, analysed separately.

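### The 17% control mortality is counted from the event in an ambulance-attended cohort and is not shown to apply to randomised patients; even at 17%, 200 per arm gives only about 54% power

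*Combined protocol and SAP*

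**What the plan says.** The Statistical analysis section sizes the randomised comparison on mortality. It begins "Given our current data showing a death rate in excess of 17% within one year of hypoglycemia", continues "we calculated that 200 individuals are needed in each of the study arms", and gives the aim as "to detect a drop in mortality to 10% in intensively monitored patients". The significance level is 0.05. Power and sidedness are not stated.

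The source of the control rate is in the Background, in unpublished Leeds data: "severe hypoglycemia, requiring emergency services intervention in 856 patients, is associated with 17.1% mortality within 12 months of the event". The same section reports recurrent severe events in more than 200 people. It also raises, as something still unclear, "whether severe hypoglycemia is more likely to occur in individuals with terminal clinical conditions".

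The Interventional study section has patients randomised and then seen on a schedule that starts at enrolment: "Face to face contact with the patient will be arranged at enrolment, 1, 3 and 12 months". The readable text gives no interval from event to enrolment, no timing of deaths after the event and no expected enrolment rate. The Statistical analysis section makes no adjustment between the cohort rate and the trial rate.

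**The concern.** The cohort and the trial differ in two ways that bear on the control rate.

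- **Time origin.** The cohort clock starts at the emergency event. The trial clock starts at enrolment, so deaths between the two count in the 17.1% but cannot occur in the trial.
- **Selection.** A trial patient has to be reached by the research nurse and take part. Patients close to death may be less likely to do so.

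Either could make standard-arm mortality lower than 17%. At a given relative reduction, a lower control rate means fewer deaths and less power. Mortality is the only outcome used for sizing. If 200 per arm is presented as sufficient when it is not, a null mortality result could be misread as evidence of no effect.

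**Working it through.** **Inputs.** Control rate 0.17 (Statistical analysis; 0.171 in the Background, 0.171 × 856 ≈ 146 deaths). Intervention rate 0.10. Significance level 0.05, taken as two-sided unless stated. 200 per arm, equal allocation.

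**Step 1: the plan's own figure.** Normal approximation with pooled variance under the null, where p̄ is the mean of p1 and p2:

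n per arm = [z(α/2)·√(2p̄(1−p̄)) + z(β)·√(p1(1−p1) + p2(1−p2))]² / (p1−p2)²

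- p̄ = 0.135, so 1.960 × √0.23355 = 0.9472.
- √(0.1411 + 0.0900) = 0.4807, and 0.8416 × 0.4807 = 0.4046.
- (0.9472 + 0.4046)² / 0.07² = 1.8273 / 0.0049 = 372.9, so **373 per arm** for 80% power.

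Power at 200 per arm = Φ[(√200 × 0.07 − 0.9472) / 0.4807] = Φ[(0.9899 − 0.9472) / 0.4807] = Φ(0.089) = **53.5%**.

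Variants do not recover 200. With 17.1% the need is 364 per arm and power at 200 is 54.6%. One-sided at 17%, the need is 294 and power at 200 is 65.8%. At 90% power, two-sided, the need is 499. Among the variants tried at 17%, exactly 200 came out only with a one-sided test, 60% power and a continuity correction.

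**Step 2: what 200 per arm can detect from 17%.** The same power formula with lower intervention rates:

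- 7.7%: Φ[(√200 × 0.093 − 0.9119) / 0.4606] = Φ(0.876) = 80.9%.
- 7.8%: Φ[(√200 × 0.092 − 0.9135) / 0.4615] = Φ(0.840) = 79.9%.

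So 80% power is reached only for a fall to about 7.7%.

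**Step 3: does a later start lower the rate?** It depends on when deaths occur.

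- *Constant hazard.* The yearly hazard is −ln(1 − 0.171) = 0.1875. For patients alive at any landmark, mortality over the next 12 months is 1 − exp(−0.1875) = 17.1%. The later start alone changes nothing.
- *Early clustering.* If a share x of attended patients die before randomisation, survivors have mortality (0.171 − x)/(1 − x) over the rest of the original 12 months. For x = 1% this is 16.3%; for x = 5% it is 12.7%. This window is shorter than 12 months from enrolment, so these values are floors for the effect of the later start. The shares x are assumptions.
- *Selection at enrolment* could lower the rate under either pattern. The documents give no figure for it.

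**Step 4: sensitivity range.** Control rates are assumed and the relative reduction is held at 1 − 10/17 = 41%. Two-sided 5%, formulas as in step 1:

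| Control | Intervention (× 10/17) | Power at 200 per arm | Per arm for 80% |
|---|---|---|---|
| 17% | 10.0% | 53.5% | 373 |
| 16% | 9.4% | 50.7% | 400 |
| 15% | 8.8% | 47.9% | 431 |
| 13% | 7.6% | 42.0% | 506 |

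**The case against.** The strongest reply is that nothing in the documents shows 17% to be wrong for the trial. With a roughly constant hazard and a full 12 months from enrolment, the later start leaves 17.1% unchanged. Adding Sheffield and enrolling people with recurrent events could move the rate either way, and the plan itself puts the rate above 17%. Figures 2 to 4 are not reproduced and the consent pages were removed, so enrolment timing may be described there. The study also calls itself preliminary, and the additional loss of power over the range shown is about 3 to 12 percentage points, on top of a shortfall that exists at 17% anyway.

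Most of this stands as a limit on the claim. It rules out saying that the control rate is certainly too high, which a reader might infer from the difference in time origin. It does not remove the gap: the rate comes from a differently defined population with a different clock, and no readable text argues that it carries over. Nor does the preliminary label help, because the section presents 200 per arm as a calculated requirement for a stated mortality difference.

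**Conclusion.** The concern holds in this form: the 17% control rate is not shown to apply to randomised patients and may be too high. Separately, the statement that 200 per arm are needed for 17% against 10% is not supported, because that comparison has 53.5% two-sided power (65.8% one-sided) and needs about 373 per arm for 80%.

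The further loss from a lower control rate is conditional. It is roughly 3 points at 16%, 6 at 15% and 12 at 13%, and rests on assumed rates and an unchanged 41% relative reduction.

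Three stronger readings are tempting but unsupported:

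- *The direction of the error is certain.* This needs deaths to cluster early or sicker patients to enrol less often. Both are plausible; neither is documented.
- *The cohort is known to contain many terminally ill patients.* The Background only asks whether this is so.
- *The standard arm could drift to 10% with no treatment effect.* From early deaths alone, (0.171 − x)/(1 − x) = 0.10 gives x = 0.071/0.9 = 7.9%. That is about 46% of all the deaths (0.079/0.171) falling before enrolment, and nothing in the documents suggests it.

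**What to change.** Before recruitment, re-derive the control rate from the existing 856-patient cohort by a landmark analysis: first event per patient, alive at the usual day of enrolment, and 12-month mortality counted from that day. Exclude patients who could not have enrolled only if the cohort data identify them; the landmark step is informative without that. If recurrent events can also lead to enrolment, say so beside the first-event rate.

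Use the resulting rate in the Statistical analysis section. State the sidedness and the power, or the detectable difference, that 200 per arm gives. Remove the description of 200 as the number needed for 17% to 10%. If the landmark rate turns out close to 17%, report that: it settles the question of applicability, and only the power statement then needs correcting.

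The cost is a small re-analysis of data the investigators already report and a less favourable stated figure. No extra patients are needed.

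### 200 patients per arm gives about 54% power, not conventional power, for the stated fall in 12-month mortality from 17.1% to 10%

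*Combined protocol and SAP*

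**What the plan says.** The Statistical analysis section ties the trial's size to the randomised part: "Power calculations were based on the interventional study". The control rate comes from local data: "Given our current data showing a death rate in excess of 17% within one year of hypoglycemia". The Background gives the underlying figure: severe hypoglycemia needing emergency services, in 856 patients, "is associated with 17.1% mortality within 12 months of the event". The conclusion drawn is that "200 individuals are needed in each of the study arms to detect a drop in mortality to 10" per cent in the intensively monitored arm, at p=0.05.

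For the analysis of a binary outcome such as death, the same section says: "For categorical data, 2X2 contingency tables will be used". The plan does not state the power, whether the test is one- or two-sided, the formula used, or any allowance for loss to follow-up.

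**The concern.** The sentence presents 200 per arm as the number required for a specific purpose. A fall from about 17% to 10% is a difference of 7 percentage points between two fairly low proportions, and 200 per arm looks small for that. Because no power is given, a reader cannot see the shortfall and will probably assume the usual 80% or 90%.

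Mortality is the only outcome used to justify the size. If power is far below 80%, a real reduction of the assumed size (41% relative, from 17.1% to 10%) would often give a non-significant result. The plan has no rule for interpreting such a result. A reader who trusted the sample size statement could take it as evidence that the benefit is absent.

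**Working it through.** **Inputs**
- Control 12-month mortality p1: just over 17% (Statistical analysis); 17.1% (Background). Both 17.0% and 17.1% are used.
- Intensive-arm mortality p2: 10% (Statistical analysis).
- n = 200 per arm, 1:1; alpha = 0.05 (Statistical analysis).
- Not stated, so assumed: two-sided test (one-sided also shown); 80% and 90% as conventional power targets; no dropout, which favours the plan.

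**Trying to reproduce 200**

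Per-arm size for two proportions, with p̄ = (p1 + p2)/2:

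n = [z(α)·√(2p̄(1−p̄)) + z(β)·√(p1(1−p1) + p2(1−p2))]² / (p1 − p2)²

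For 17.1% v 10%, p̄ = 0.1355, two-sided 5%, 80% power:
- first term: 1.960 × √(2 × 0.1355 × 0.8645) = 0.9487
- second term: 0.8416 × √(0.171 × 0.829 + 0.10 × 0.90) = 0.4052
- n = (0.9487 + 0.4052)² / 0.071² = 363.6, so 364

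| Setting | n per arm, control 17.0% | n per arm, control 17.1% |
|---|---|---|
| Two-sided 5%, 80% power | 373 | 364 |
| Two-sided 5%, 90% power | 499 | 487 |
| Two-sided 5%, 80%, continuity-corrected | 401 | 392 |
| One-sided 5%, 80% power | 294 | 287 |

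None of these gives 200; the smallest is 287.

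**Power actually available with 200 per arm**

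Power = Φ{[(p1 − p2) − z(α)·SE0] / SE1}, with SE0 = √(2p̄(1−p̄)/n) and SE1 = √{[p1(1−p1) + p2(1−p2)]/n}.

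- 17.1% v 10%: SE0 = 0.03423, SE1 = 0.03404. (0.071 − 1.960 × 0.03423)/0.03404 = 0.115, so power = 54.6%.
- 17.0% v 10%: SE0 = 0.03417, SE1 = 0.03399. (0.070 − 1.960 × 0.03417)/0.03399 = 0.089, so power = 53.5%.
- One-sided 5% (1.645 in place of 1.960): 66.7% and 65.8%.

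**Does the choice of test matter?** Two-sided, 17.1% v 10%, 200 per arm:

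| Method | Power |
|---|---|
| Pooled normal formula | 54.6% |
| Unpooled variance | 55.0% |
| Arcsine | 55.2% |
| Chi-square, exact enumeration | 55.1% |
| Continuity-corrected | 48.7% |
| Fisher exact, enumeration | 49.3% |
| Log-rank (hazard ratio ln 0.90/ln 0.829 = 0.562; 54.2 expected deaths) | 56.5% |

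**Does the control rate matter?** Against 10%, two-sided power is 63.6% at a control rate of 18%, 72.6% at 19% and 80.2% at 20%. If 17.1% of 856 is about 146 deaths, the upper 95% limit for that rate is 19.7%, where power is still 78%.

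**What 200 per arm can do**
- Starting from 17.1%, 80% power is reached when p2 falls to 7.87%: SE0 = 0.03305, SE1 = 0.03273, (0.0923 − 1.960 × 0.03305)/0.03273 = 0.84. That is a relative reduction of 1 − 7.87/17.1 = 54%, against the assumed 1 − 10/17.1 = 41%.
- If the observed rates were exactly 17.1% and 10%, the 95% confidence interval for the difference would be 7.1 ± 1.960 × 3.404 points, about 0.4 to 13.8 points.
- If enrolled patients had lower control mortality than the source cohort (assumed 13–15%) and the same relative reduction, power would be 43–49%.

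**The case against.** The best defence is that the plan states no power, so 200 contradicts no declared target. Read very literally, the sentence might mean only that the assumed difference, if observed, would be significant: 34/200 v 20/200 gives an uncorrected chi-square p of 0.041. It is true that no stated power is contradicted. But that reading amounts to planning for roughly 50% power (179 to 184 per arm, or 206 to 211 with continuity correction). A size justified that way should say so, because few readers would take a number described as needed to mean roughly even odds of success.

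Second, the control rate is worded as exceeding 17%, without an upper bound. The only figure given is 17.1%, and two-sided 80% power requires about 20%, which the documents do not support.

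Third, the interventional part is called preliminary, and the Aims list hypoglycemic events and confidence or quality of life ahead of clinical outcome. This softens the consequence for the trial as a whole. It does not correct the sentence, because the size rests on mortality and nothing else.

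The origin of 200 is unknown. A comparison of 20% with 10% at 80% power gives 199, and a one-sample test of 10% against a fixed 17% gives 199.5. The first does not use the stated control rate; the second ignores sampling error in the control arm. Neither is documented, and the conclusion depends on neither.

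**Conclusion.** The concern holds. With the plan's own rates, 200 per arm gives about 54% power with a two-sided 5% test (48–57% across the methods tried) and about 67% one-sided. Conventional 80% power needs 364 to 373 per arm two-sided, or 287 to 294 one-sided. The description of 200 as the number needed is therefore not supported at 80% or 90% power, with either sidedness.

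The result assumes a control rate of 17.0–17.1%, equal allocation and complete 12-month follow-up. Any loss to follow-up would lower the power further. The missing power and sidedness are part of the same defect, since they conceal the shortfall. This should be corrected before the sample size statement is relied on.

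**What to change.** Replace the sample size sentence in Statistical analysis with:

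> With 200 patients per arm, a two-sided 5% test has about 54% power to detect a fall in 12-month mortality from 17.1% to 10%, and 80% power for a fall to 7.9% or lower. Mortality will be reported as a difference with a 95% confidence interval, and a non-significant result will not be read as absence of effect.

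The two-sided test is an assumption of this wording, since the plan is silent, and the sponsor should confirm it. If a one-sided test was intended, that should be stated and justified, and the power figure becomes about 67%. The formula used should be named so that the figure can be checked.

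The cost is wording only: no extra patients and no change to design or conduct. The price is a less favourable stated power.

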### **Hypothesis**

Inadequate education, infrequent glucose testing and clinical co-morbidities in subjects with diabetes are associated with severe hypoglycemic episodes. Therefore, structured diabetes specialist input with regular glucose testing is important to reduce the risk of severe hypoglycemia.

[figure not shown]

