### **Aims**

The proposed work is divided into two parts through an observational and an interventional study.

1. Observational study: characterise individuals with severe hypoglycemia.
2. Interventional preliminary study: investigate the effect of regular glucose monitoring and specialist nurse input into a) future hypoglycemic events, b) confidence with diabetes management/quality of life and c) clinical outcome.

[figure not shown]

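### No primary outcome is named in the available text, and the trial is sized on 12-month mortality while its hypothesis is about severe hypoglycemia

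*Combined protocol and SAP*

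**What the plan says.** Four places in the combined protocol and SAP bear on this.

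- **Hypothesis.** The statement about the intervention is that "structured diabetes specialist input with regular glucose testing is important to reduce the risk of severe hypoglycemia".
- **Aims.** The second aim, the interventional part, is to study the effect on "a) future hypoglycemic events, b) confidence with diabetes management/quality of life and c) clinical outcome". The three items are not ranked, and death is not mentioned by name.
- **Interventional study.** The key to Figure 4 adds major adverse cardiovascular events. It also says that hypoglycemia frequency belongs to the 12-month clinical outcome but is analysed separately.
- **Statistical analysis.** The power calculation starts from "a death rate in excess of 17% within one year of hypoglycemia", and concludes that "200 individuals are needed in each of the study arms" "to detect a drop in mortality to 10% in intensively monitored patients", at p=0.05. Power, sidedness and dropout are not given. The section then assigns tests by data type. It designates no primary outcome, testing order, split of the significance level or adjustment.

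The only figure in the documents on repeat severe hypoglycemia is in Background: "in excess of 200 individuals had recurrent severe hypoglycemic events".

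**The concern.** The outcome that fixes the size of the trial is not the outcome that its hypothesis is about. Adding the word primary somewhere does not settle this. Beside mortality, it leaves the hypothesis unsized; beside hypoglycemia, it leaves 200 per arm without a justification. The sponsor has to choose.

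Until it does, nothing says which result carries the conclusion. A trial with no clear mortality difference but a favourable hypoglycemia or questionnaire result is a realistic prospect. The plan gives no way of saying in advance whether that is a positive trial, a negative one or a lead for further work. With several candidate outcomes, the chance that at least one favours the intervention by luck exceeds the nominal 5%.

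**Working it through.** **1. The plan's own sample size.** Inputs from Statistical analysis: control 0.17, intensive 0.10, significance level 0.05. Assumed, because not stated: two-sided test, 80% power, no dropout. The mean proportion is 0.135.

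n per arm = [1.96 × √(2 × 0.135 × 0.865) + 0.8416 × √(0.17 × 0.83 + 0.10 × 0.90)]² / 0.07²
= (0.947 + 0.405)² / 0.0049 ≈ 373.

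The stated 200 is not reproduced. A one-sided test needs 294, and 90% power two-sided needs 499. Starting from the cohort's 17.1% (Background) gives 364 two-sided at 80%.

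**2. Power of 200 per arm for mortality.**

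Standard error under no difference = √(2 × 0.135 × 0.865 / 200) = 0.0342, and 1.96 × 0.0342 = 0.0670.
Standard error under the alternative = √((0.1411 + 0.0900) / 200) = 0.0340.
Power = Φ((0.0700 − 0.0670) / 0.0340) = Φ(0.089) ≈ 54%.

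From 17.1% the power is 55%; one-sided from 17% it is 66%.

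**3. False-positive risk with unranked outcomes.** This takes three outcomes (hypoglycemia, questionnaire, mortality/cardiovascular events), each tested at 5%. That is an assumption, because the plan states a level only for the mortality sizing.

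- Independent: 1 − 0.95³ = 14.3%.
- Pairwise correlation 0.5 (simulation): 12.5%.
- Pairwise correlation 0.8 (simulation): 9.9%.

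**4. What 200 per arm could detect for recurrent severe hypoglycemia.** The documents give no 12-month control rate. If the 200 or more people with recurrence came from the cohort of 856, the proportion is at least 200 / 856 = 23.4%. Neither that denominator nor the period is stated, so a range is needed. Simple proportions, two-sided 5%, about 80% power, before any allowance for deaths:

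| Assumed control rate | Detectable intensive-arm rate | Relative reduction |
|---|---|---|
| 15% | 6.4% | 57% |
| 20% | 10% | 50% |
| 23.4% | 12.6% | 46% |
| 30% | 18% | 40% |

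**5. Does hypoglycemia give more power than mortality?** The mortality target is a relative reduction of 1 − 10/17 = 41%. The same reduction in recurrence has 70% power at 23.4% (to 13.8%), but about 48% at 15% (to 8.8%), below the 54% for mortality. The ordering therefore depends on a rate that the documents do not give.

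**6. Deaths.** At the plan's rates, about 0.17 × 200 = 34 control patients and 0.10 × 200 = 20 intensive patients would die within 12 months. A plain proportion with a further event would count those who died first as event-free, and more of them would be in the control arm.

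**The case against.** The strongest reply is that mortality is the implied primary outcome, since it alone has a target difference and a significance level, and that the interventional part is called preliminary, where strict error control matters less. Part of this stands. The label does soften the false-positive concern, and the reading of mortality as primary is possible. But the text never says so, and that reading makes the gap with Hypothesis and Aims wider. A calculation meant to detect a mortality difference at p=0.05 is also a hypothesis-testing use of the trial. A label in Figures 3 or 4 cannot be excluded, though Aims and Statistical analysis, where it belongs, are available and carry none.

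Several stronger readings are tempting and should not be drawn:

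- A reader might infer that the plan tests every outcome at 5% and declares success on any of them. It contains no success rule, and p=0.05 appears once, with the mortality sizing. The 14% is conditional, assumes independence, and depends on counting three outcomes.
- A reader might take the first aim as support. That aim is the observational part. The relevant item is (a) of the interventional aim, which speaks of hypoglycemic events and does not say severe.
- A reader might infer that hypoglycemia is the better-powered choice. Step 5 shows that this reverses at a lower recurrence rate, and nothing in the documents says that both outcomes would fall by the same proportion.

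**Conclusion.** The point holds in this form: in the available text no primary outcome is designated, and the sizing outcome (12-month mortality) differs from the outcome of the hypothesis (severe hypoglycemia) and from item (a) of the interventional aim (hypoglycemic events). It should be corrected.

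Its size has two parts. The mortality comparison has about 54% power at 17% against 10%, assuming a two-sided 5% test and no dropout. The chance of at least one false positive is up to about 14% if three outcomes are each tested at 5%, and about 12.5% at correlation 0.5. The case for hypoglycemia as primary rests on Hypothesis and Aims, not on a power advantage.

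**What to change.** In Aims and Statistical analysis:

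1. Name one primary outcome that matches the hypothesis: further ambulance-attended severe hypoglycemia within 12 months of randomisation, taken from ambulance records in both arms and tested two-sided at 5%. The ambulance reporting pathway under Plan of investigation offers the same source for both arms. That matters because the intensive arm has repeated nurse contacts and the standard arm has one.
2. State how death before an event is handled, for example as a competing risk, so that it is not counted as event-free.
3. Make mortality, the questionnaire, HbA1c and cardiovascular events secondary, reported with confidence intervals and no confirmatory claim.
4. State that 200 per arm was derived from mortality and gives about 54% power for 17% against 10% (two-sided 5%).
5. Give the detectable difference for the new primary from the sponsor's own 12-month recurrence rate. Until that rate is supplied, show the range in the table above.

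If the sponsor prefers mortality as primary, it should say so, restate the power as about 54%, and make hypoglycemia secondary.

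The cost is some protocol text, one tabulation from a cohort that the sponsor already holds, and a short analysis specification for deaths. It adds no visits or patients at the planned 200 per arm. The downside is that a mortality difference could no longer be the confirmatory result. At low recurrence rates, 200 per arm would also detect only a large reduction in hypoglycemia, and the plan would have to say so.
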